2.4.3.4 Compliance with key study activities

For the following endpoints, descriptive statistics will be calculated including the number of available data, mean, SD, median, minimum, and maximum by study conduct approach group.

- The number of times the patient used the Bluetooth devices in accordance with the study instructions from baseline to Week 24. Qualitative deviations will be used to collect this information.
- Number of times the patient completed the blood draw visits (Visit 10 and Visit 12) in accordance with the study instructions will be based on the protocol deviations.

Number of patient withdrawal during the treatment period (from Day 1 to Week 24) will be described in patient disposition [Section 2.2](#).

2.4.4 Analyses of efficacy endpoints

For statistics where international and conventional units do not impact the results (eg, means and least square (LS) means for percent changes from baseline, p-values for both percent and absolute changes from baseline, rates of patients below a threshold), derivations will be done and statistical models will be run using conventional units. For other statistics (eg, descriptive statistics at baseline and over time, absolute changes from baseline), derivations will be done with both international and conventional units.

Figures will be provided with 2 different axes by parameter when applicable. For example, for HbA1c, figures will be presented by % and mmol/mol.

2.4.4.1 Analysis of primary efficacy endpoint(s)

2.4.4.1.1 Primary efficacy analysis

The primary efficacy variable, change in HbA1c from baseline to Week 24 in % as defined in [Section 2.1.3.1](#) will be analyzed in the ITT population using available data during the 24-week randomized period (defined in [Section 2.1.3](#), used to assess the ITT estimand). A mixed-effect model with repeated measures (MMRM) approach will be used, under the missing at random

framework carried out via SAS PROC MIXED using an adequate contrast at Week 16 and Week 24).

The model will include fixed categorical effects of study conduct approach group (Virtual, Traditional), visit (Week 16, Week 24), study conduct approach-by-visit interaction, visit-by-study conduct approach-by-baseline HbA1c interaction, randomization stratum of site as well as, the continuous fixed covariates of baseline HbA1c value and baseline HbA1c value-by-visit interaction.

This model will be run with an unstructured correlation matrix to model the within-patient errors.

Parameters will be estimated using restricted maximum likelihood method with the Newton-Raphson algorithm. Denominator degrees of freedom will be estimated using Satterthwaite's approximation.

This model will provide baseline adjusted least squares (LS) means estimates at Week 24 for both study conduct approach groups, as well as, the differences of these estimates, with their corresponding standard error (SEs) and 95% CIs.

This analysis will be performed using the randomization strata as per IVRS.

No formal comparison and no p-value will be provided.

Model assumption checks

As no formal comparison the analysis of the residuals of MMRM based on studentized residuals will be not performed.

2.4.4.1.2 Subgroup analyses

Where appropriate for the size of a subgroup, exploratory analyses will be performed on the primary endpoint to summarize the treatment effects across subgroups.

For each subgroup, the primary efficacy variable will be analyzed in the ITT population using post-baseline HbA1c data available on the 24-week randomized period, (to assess the ITT estimand). A similar MMRM approach as described for primary analysis will be applied adding the corresponding subgroup factor, subgroup factor-by-study conduct approach arm interaction, subgroup factor-by-visit interaction and subgroup factor-by-visit-by study conduct approach arm interaction.

The subgroups will be defined by the following baseline and screening factors:

- Age group (<65, [65-75[and ≥ 75 years).
- Gender (male, female).
- Baseline BMI (<25, [25-30[, [30-40[and ≥ 40 kg/m²).
- Randomization stratum of screening HbA1c (<7.6%, $\geq 7.6\%$).
- Randomization stratum of site, ("only if the size of the subgroup will be relevant,"
- Duration of diabetes (<10, ≥ 10 years).
- Baseline estimated GFR categories (mL/min/1.73m²): (<60; ≥ 60).

If the subgroup factor is a randomization stratification factor, then the strata as per IVRS will be used.

The randomization strata of screening HbA1c and site will not be included in the model.

Least Square Means Difference Virtual versus Traditional approach at Week 24 will be provided, as well as the corresponding SEs and 95% CI, within each subgroup. The significance level of the study conduct approach-by-subgroup factor interaction term at Week 24 will be not provided for each factor as no formal comparison. Forest plots will be provided.

Subgroups analyses using randomization strata derived as per electronic case report form (e-CRF), should be performed only if necessary (in case of high number of discrepancies between stratum as per IRT and stratum as per e-CRF) and should be considered as sensitivity analysis.

Further subgroup analyses may be performed if deemed necessary for interpretation of results.

2.4.4.2 Analyses of secondary efficacy endpoints

Secondary efficacy endpoints are described in [Section 2.1.4](#).

All secondary efficacy endpoints will be analyzed or summarized on the 24-week randomized period (to assess the ITT estimand) using the ITT population.

The following secondary efficacy endpoints will be analyzed using the same model (same analysis) as the one used for primary endpoint (MMRM model) as described in [Section 2.4.4.1.1](#).

- HbA1c (%): change from baseline to Week 16;

The following secondary efficacy endpoints will be analyzed using the same approach as the one used for primary endpoint (MMRM model) as described in [Section 2.4.4.1.1](#). The model will include fixed categorical effects of study conduct approach group, visit, study conduct approach-by-visit interaction, randomization stratum of site, randomization stratum of HbA1c (<7.6 % and ≥ 7.6%), the continuous fixed covariates of the corresponding baseline value, and baseline value-by-visit interaction.

- FPG: change from baseline to Week 16 and Week 24;
- Change in mean 24-hour plasma glucose based on 7-point SMPG from baseline to Week 16 and Week 24;

For the model on change in FPG and on the mean 24-hour plasma glucose based on 7-point SMPG, the visit term has 2 levels (Week 16 and Week 24).

No formal comparison and no p-value will be provided.

The following secondary endpoints will be analyzed using descriptive measures:

- Change in 7-point SMPG profiles per time-point from baseline to Week 16 and Week 24;

For all continuous endpoints, observed values and change from baseline will be also described for all visits with mean, median, SD, minimum and maximum. A figure representing the mean (+/- SE) change from baseline at each visit will be produced by study conduct approach group.

2.4.4.3 Multiplicity issues

No formal comparison and no p-value will be provided; 95% CIs presented for these endpoints will be calculated for descriptive purpose only.

2.4.4.4 Additional efficacy analyses

Not applicable.

2.4.5 Analyses of safety data

The summary of safety results will be presented by study conduct approach group.

General common rules

All safety analyses will be performed on the safety population as defined in [Section 2.3.2](#), unless otherwise specified, using the following common rules:

- Safety data in patients who do not belong to the safety population (eg, exposed but not randomized) will be listed separately
- The baseline value is defined as the last available value prior to the first injection of IMP.
- When the time of assessment is not available, the value is considered as baseline if assessment date is the date of 1st IMP intake.
- For clinical vital signs only, the potentially clinically significant abnormality (PCSA) values are defined as abnormal values considered medically important by the Sponsor according to predefined criteria/thresholds based on literature review and defined by the Sponsor (PCSA criteria will be provided in the ADaM metadata).
- For clinical vital signs only, PCSA criteria will determine which patients had at least 1 PCSA during the TEAE period, taking into account all evaluations performed during the TEAE period, including nonscheduled or repeated evaluations. The number of all such patients will be the numerator for the on-treatment PCSA percentage.
- For clinical vital signs only, the treatment-emergent PCSA denominator by group for a given parameter will be based on the number of patients assessed for that given parameter in the treatment-emergent adverse event period by study conduct approach group on the safety population.
- For quantitative safety parameters based on central laboratory/reading measurements, descriptive statistics will be used to summarize results.
- The analysis of the safety variables will be essentially descriptive and no systematic testing is planned.

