10.1.2 Randomization Visit (Visit 2)

10.1.2.1 Visit 2-Step 1 (Week -1)

Visit 2-Step 1 telephone call will occur about 1 week after Visit 1-Step 2 when the investigator has received laboratory reports for the screened patients in order to assess exclusion criteria [E 03](#) and [E 12 \(Section 7.2\)](#). The eligible patients will be randomized to the study group through IRT.

Appropriate study materials will be shipped to eligible patients: Bluetooth blood glucose meter with associated accessories (lancets, control solutions, test strips etc.), e-diaries features, and instructions. Bluetooth devices (pulse oximeter, BP cuff, and scale) will be shipped to patients allocated to the virtual group. Bluetooth devices are listed in Appendix E.

Patients of the virtual group will record any symptoms in the eDiary so that the investigator is informed through the study website portal and will record the AE into the e-CRF.

An onsite visit will be scheduled within a week (+/- 4 days) for the traditional group.

Patient randomized in the virtual group will also be scheduled for an onsite visit, but for physical examination only. The virtual Visit 2-Step 2 visit will be scheduled within 1 week (+/- 4 days) of the Visit 2-Step 1 for the virtual group.

Patients should be reminded to perform at least one day of 7-point SMPG prior to the Visit 2-Step 2 visit. Patients of the traditional group will be reminded to bring the glucose meter to the study visit.

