10.1.4 Onsite/virtual visits (V6, 8, and V10) during treatment period

Three study visits will occur onsite before the EOT for the traditional approach group. Virtual approach group patients will have the corresponding visit as virtual visit.

During these visits, study material (eg, ancillaries and glucose meter accessories) and IMP will be dispensed or shipped, and the patients' progress, SMPG patterns, dose regimens and data collected during the study (eg, hypoglycemia, AE/SAE, average fasting and postprandial SMPGs over the past days) will be discussed. For patients of the traditional group, the IMP dispensation will be done on site by the investigator or pharmacist. For patients of the virtual group, the IMP will be shipped using the DTP service described in [Section 8.1.3](#).

Patients of the traditional group will bring their glucose meter and IMP boxes to the study site at each onsite visit. For patients of the virtual group, the used and unused IMP will be returned to the sites by Marken driver.

Patients of the virtual group will perform all assessments via virtual device for vital signs (BP, HR) and weight measurements.

The investigators and study staff will check and document in the source data if the patient has reached the titration goal or not at each visit. Appropriate titration will be continued until target fasting SMPG without hypoglycemia has been reached.

Investigational medicinal product compliance (collecting and counting used and unused cartridges and syringes) will be checked and addressed with the patients. The IMP compliance will be checked by video chat between the patients of the virtual approach group and the site staff.

Consultation for diet and life-style modification should be provided during the visits if needed.

Overall Study Experience-Sites part 1 questionnaire (resource requirement) should be completed by the Investigator.

Within 1 week prior to Visit 10, patients should be reminded, if needed, to perform at least one day of 7-point SMPG.

Resource use questionnaire will be completed by the patients at Visits 6, 8, and 10.

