10.2 DEFINITION OF SOURCE DATA

10.2.1 Source data to be found in patient's file

For both patient groups, all evaluations recorded in the e-CRF must be supported by appropriately signed source documentation related but not limited to the following:

- Agreement and signature of informed consent form with the study identification; the signed electronic informed consent form will be printed from the study web portal
- Study identification (name)
- Patient number, confirmation of randomization, approach group, treatment batch number, dates and doses of study medication administration
- Medical, surgical, diabetes history, including information on :
 - Demography, inclusion and exclusion criteria
 - Last participation in a clinical trial
 - Contraception method for WOCBP
 - Previous and concomitant medication
- Dates and times of visits and assessments including examination results (vital signs, height, body weight, laboratory reports)
- For patients of the virtual group, the data transferred directly from Bluetooth devices to the study web portal will be considered as source data and will not have to be recorded in the patient file
- Insulin dose (both basal and mealtime) titration assessment and recommendation for insulin dose adjustment
- Investigator/physician notes, nursing notes, dietician's notes
- AEs and AEs follow-up,
 - In case of SAE, the site should file in the source documents at least copies of the hospitalization reports and any relevant examination reports documenting the follow-up of the SAE
- Date of premature study discontinuation (if any) and reason.
- Patient eDiaries

A monitor will visit the sites to verify the accuracy of the source data listed above against patient's files.

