11.4.3.4.3 Vital signs and physical examination

The potentially clinically significant abnormality (PCSA) values are defined as abnormal values considered medically important by the Sponsor according to predefined criteria/thresholds based on literature review and defined by the Sponsor for vital signs

Potentially clinically significant abnormality criteria will determine which patients had at least one PCSA during the TEAE period, taking into account all evaluations performed during the on-treatment TEAE period, including unscheduled or repeated evaluations. The number of all such patients will be the numerator for the PCSA percentage during the TEAE on-treatment period

The incidence of PCSAs at any time during the TEAE period will be summarized by approach group whatever the baseline level and according to baseline status.

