2.4.5.5 Analyses of vital sign variables

The summary statistics (including number, mean, median, standard deviation, minimum and maximum) of all vital signs variables blood pressure, heart rate and body weight (and changes from baseline) will be calculated for each visit or study assessment (baseline, each post baseline time point, last on-treatment) by study conduct approach group.

The incidence of PCSAs at any time during the treatment-emergent adverse event period will be summarized by study conduct approach group irrespective of the baseline level and/or according to the following baseline status categories:

- Normal/missing.
- Abnormal according to PCSA criterion or criteria.

The change in body weight from baseline to Week 24 will be analyzed in the safety population using a similar MMRM model as described in [Section 2.4.4.1.1](#).

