2.5.5 Unscheduled visits

The analysis windows mentioned in [Section 2.5.4](#) will be applicable to re-allocate the unscheduled assessments (measurements from the central laboratory only) for HbA1c and FPG assessments.

After applying the time windows as mentioned in [Section 2.5.4](#), if two assessments are associated to the same time point, the closest from the targeted study day is used. In case of equality, the earliest measurement is used.

The determination of baseline for HbA1c and FPG variables is based on all measurements from both scheduled and unscheduled visits (measurements from the central laboratory only). The determination of baseline for safety parameters is based on all assessments from both scheduled and unscheduled visits too. The determination of the last on-treatment value for safety parameters is also based on all assessments from both scheduled and unscheduled visits. Measurements from the unscheduled visits (including results from local laboratory when no corresponding central laboratory results are available) are also considered for PCSA summary of safety parameters.

Unscheduled visit measurements are not included in the by-visit summaries.

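### Vital-sign PCSA incidence counts every on-treatment reading, so the comparison by approach is open to unequal ascertainment if extra home-device readings from the virtual arm are captured

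*SAP*

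**What the plan says.** **The counting rule.** SAP 2.4.5 determines which patients had at least one vital-sign PCSA "taking into account all evaluations performed during the TEAE period, including nonscheduled or repeated evaluations". Protocol 11.4.3.4.3 has the same rule: "taking into account all evaluations performed during the on-treatment TEAE period, including unscheduled or repeated evaluations". SAP 2.5.5 adds that measurements from unscheduled visits "are also considered for PCSA summary of safety parameters", although the same section leaves them out of the by-visit summaries.

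**The denominator and the display.** The denominator is "based on the number of patients assessed for that given parameter in the treatment-emergent adverse event period", so a patient measured once and a patient measured many times weigh the same. SAP 2.4.5.5 gives the table: "The incidence of PCSAs at any time during the treatment-emergent adverse event period will be summarized by study conduct approach group".

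**Who measures, and when.** Protocol 10.1.2.1 states that "Bluetooth devices (pulse oximeter, BP cuff, and scale) will be shipped to patients allocated to the virtual group". Protocol 10.1.1 has later blood pressure taken by the patients themselves in the virtual group and by site staff in the traditional group. For Visits 6, 8 and 10, protocol 10.1.4 says "Patients of the virtual group will perform all assessments via virtual device for vital signs (BP, HR) and weight measurements". Protocol 10.1.5 schedules vital signs at Visit 12 in both groups. Under protocol 10.2.1, for the virtual group, "the data transferred directly from Bluetooth devices to the study web portal will be considered as source data".

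**The concern.** The chance of at least one abnormal value rises with the number of values examined, even when the underlying blood pressure, heart rate and weight are the same. This trial randomizes how patients are followed and measured. One arm has measuring devices within reach for 24 weeks. The other is measured by staff at visits. An incidence that depends on the number of readings can therefore reflect intensity of observation as well as harm.

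The safety of patients managed under the two approaches is a stated secondary objective (protocol 5.2, SAP 1.2.2). If unscheduled device readings reach the analysis dataset, the PCSA table could show more abnormal vital signs in the virtual arm only because more were recorded. Nothing in the table would reveal this, since the number of readings per patient is not reported.

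**Working it through.** **Step 1. Scheduled readings.** Protocol section 10 states 5 onsite and 7 telephone visits for the traditional group. The visit schedule reproduces this: onsite at Visits 2-Step 2, 6, 8, 10 and 12 (5); telephone at Visits 3, 4, 5, 7, 9, 11 and 13 (7). Removing the baseline visit leaves 5 − 1 = 4 onsite on-treatment visits. Protocol 10.1.4 and 10.1.5 and SAP Appendix B schedule vital signs at those same four visits in the virtual arm. On schedule alone the count is 4 against 4, and the expected incidence ratio with no true difference is 1.00.

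**Step 2. Is there a rule for other home readings?** SAP 2.5.4 Tables 2 and 3 give analysis windows for the questionnaires, HbA1c and FPG, but none for vital signs. The closest-to-target-day rule in SAP 2.5.5 follows those windows. The mean of two blood pressure readings is described for the screening measurement (protocol 10.1.1) and is not restated for home readings. The documents do not say which device readings enter the PCSA table.

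**Step 3. Effect of extra readings, systolic pressure.** The SAP Appendix A criteria are at least 160 mmHg with a rise of at least 20, or at most 95 mmHg with a fall of at least 20. The other inputs are assumptions, identical in both arms: true mean 126, between-patient SD 12 and within-patient SD 9 mmHg, the last applying to the baseline value and to each later reading. By simulation, the percentage with at least one PCSA is:

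| Readings | Relation among extra readings | Incidence |
|---|---|---|
| 4 (schedule only) | none | 3.2% |
| 8 (one extra per visit) | independent | 5.7% |
| 8 (one extra per visit) | about 65% of within-patient variance shared within a day | 5.1% |

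The ratios are 5.7/3.2 = 1.8 and 5.1/3.2 = 1.6. With within-patient SD 6, incidence is about 0.3% at 4 readings and 0.65% at 8 independent readings. With SD 12 it is 9.5% and 16.5%. The level depends heavily on the assumed SD; the direction does not.

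**Step 4. Second method.** Take p as the chance that one reading meets a criterion. With independent readings, P(at least one in k) = 1 − (1 − p)^k. At an assumed p = 1%:

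- k = 4: 1 − 0.99^4 = 3.9%
- k = 8: 1 − 0.99^8 = 7.7%, ratio 1.96

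With a beta-binomial model and within-patient correlation 0.3, the figures are 2.7% and 3.8%, ratio 1.44. Over p = 0.5% to 5% and correlation 0 to 0.3, the ratio at 8 readings runs from 1.4 to 2.0.

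**Step 5. In patients.** At the planned 75 per arm, 3.2% against 5.7% is 2.4 against 4.3 patients, a difference of about 1.9. SAP section 2 reports 15 randomized, so about 7.5 per arm if the arms are near equal (the split is not given). The same difference is then 0.025 × 7.5 = 0.19 of a patient.

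**The case against.** The strongest case against is that nothing shows the extra readings exist. No section asks virtual-arm patients for blood pressure, heart rate or weight readings beyond the four scheduled visits, and the device-use endpoint is defined as use in line with study instructions. Calling device transfers source data settles where the original record lies. It does not put every transmission into the analysis dataset. SAP 2.5.4 names the e-diary streams that arrive without a protocol visit (SMPG, insulin doses, questionnaires), and vital signs are not among them. Protocol section 10 allows unscheduled onsite or Homecare safety visits in both groups, so the traditional arm is not capped at four readings. The by-visit summaries in SAP 2.4.5.5 already compare the arms on scheduled values. A PCSA table is also meant to be inclusive.

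Most of this stands. A reader might infer that the comparison is biased by design. The documents do not support that: the schedule is balanced, and unequal ascertainment needs extra readings to be both taken and captured. A reader might also infer that self-taken readings are noisier than staff readings. The documents say nothing on this, and they provide for a common reference arm and for guidance on device use.

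What the objection does not remove is the gap in the rule. It admits any reading, only one arm holds the devices, and nothing equalizes or reports the counts. Requiring both a level and a change limits false flags for heart rate and blood pressure, but it does not end the dependence on reading count. The weight criterion is a 5% change alone.

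**Conclusion.** The rule leaves the PCSA comparison by approach open to differential ascertainment, most likely upward in the virtual arm, if home readings beyond the scheduled visits are captured. It does not establish that bias is present. Under the assumed systolic distribution, one extra reading per visit moves incidence from about 3.2% to between 5.1% and 5.7% with no true difference. These figures rest on an assumed mean, assumed SDs and an assumed number of readings, none of which the documents give, so they illustrate the mechanism and do not estimate its size here.

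Practical weight is low. SAP 2.4.5 describes the safety analysis as essentially descriptive, and SAP section 2 limits reporting to basic descriptive tables or listings after early termination with 15 patients randomized. In so small a table one extra flagged patient is 1/8 to 1/7 of an arm (12.5% to 14.3%, if the arms are near equal), so readers should be able to see how many readings lie behind each count.

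**What to change.** In SAP 2.4.5 and 2.4.5.5:

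- Base the between-approach PCSA comparison on one value per parameter per scheduled on-treatment visit (Visits 6, 8, 10 and 12) in both arms, chosen by the same rule in each arm and without regard to the value.
- Keep the all-readings PCSA table or listing as a safety screen. This also preserves the analysis in protocol 11.4.3.4.3.
- Next to it, report the number of readings per patient by arm for each parameter.

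The cost is a wording change, one filter on the vital-signs data and one count. It needs no new data collection; averaging of repeat home blood pressure readings should not be imposed now, because that would change how data are collected. The downside is that an abnormality seen only between visits is absent from the comparative table. It stays in the inclusive table or listing and in adverse event reporting.
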